4.5.2 Definition of treatment-emergence

Values will be considered treatment-emergent if they start within 2 calendar days after the last day of study drug administration, i.e. the treatment-emergent window will be 2 days.

4.5.3 Definition of regions

The following regions are used for further subgroup analyses:

- Europe and Australia/New Zealand: Belgium, Netherlands, Switzerland, Germany, Czech Republic, Hungary, Turkey, Spain, Italy, France, UK, Australia, and New Zealand
- North America: US and Canada
- East Asia: Japan.

4.6 Unblind Review

The results of the unblinded validity review meeting will be documented in the Validity Review Report.

5. Analysis Sets

5.1 Assignment of analysis sets

Long term safety analysis set will be used in LTE phase. It will consist of all patients randomized and treated with study medication (FAS), who have continued treatment with study medication in the LTE phase of the study.

6. Statistical Methodology

Although dose titration is in use, the descriptive analyses will be shown to the following treatment groups:

- Patients randomized to riociguat in the main phase who stayed on riociguat in the LTE phase (called Riociguat-Riociguat in outputs)
- Patients randomized to placebo in the main phase who switched to riociguat in the LTE phase (called Placebo-Riociguat in outputs)
- Total of all patients.

Any comparison between the two treatment groups defined above should be done very carefully, since all patients received riociguat in the LTE phase (ie. initial randomization is not preserved). The decision whether or not a patient takes part in the LTE phase may depend on the treatment which was given in the main phase and thus the groups may not be comparable. All results are purely exploratory.

Number of decimal places for summary statistics will be the following:

Figure 6–1 - Decimal places for summary statistics

Statistic	Number of digits
Minimum, maximum	Same as original data
Mean, median	1 more than in original data
SD	2 more than in original data
Frequencies (%)	1 decimal place

6.1 Population characteristics

6.1.1 Demographics and baseline characteristics

Demographic variables and baseline characteristics will be summarized by treatment group and overall for long term safety analysis population.

The following demographic data will be recorded:

- Date of birth (month and year) (age)
- Sex
- Ethnicity

- Smoking status, including number of cigarettes per day
- Alcohol consumption

Summary statistics (number of data available and missing data, mean, standard deviation, minimum, median and maximum) will be presented for continuous variables. Frequency tables will be presented for categorical variables. Smoking history and status will be summarized. Age will be summarized as a continuous variable and as a categorical variable categorized into two groups (< 65 years, ≥ 65 years).

6.1.2 Medical history and concomitant medication

Medical history (MH) and concomitant medication (CM) will be summarized by treatment group and overall.

Medical history findings will be coded by Medical Dictionary for Regulatory Activities (MedDRA) codes. System organ class (SOC) and preferred term (PT) will be used in tabulations.

Medical history findings (i.e., previous diagnoses, diseases or surgeries) meeting all criteria listed below will be collected:

- Pertaining to the study indication
- Started before signing of the informed consent
- Considered relevant to the study
- Medical history related to concomitant therapy

In the following differentiation between medical history and AEs, the term “condition” may include abnormal e.g., physical examination findings, symptoms, diseases, laboratory, ECG.

- Conditions that started before signing of informed consent and for which no symptoms or treatment are present until signing of informed consent are recorded as medical history (e.g., seasonal allergy without acute complaints).
- Conditions that started before signing of informed consent and for which symptoms or treatment are present after signing of informed consent, at unchanged intensity, are recorded as medical history (e.g., allergic pollinosis).
- Conditions that started or deteriorated after signing of informed consent will be documented as AEs.

Prior and concomitant medications will be coded by Anatomical Therapeutic Chemical (ATC) classification system according to the World Health Organization Drug Dictionary (WHO-DD). The ATC class is taken from the WHO-DD code (first character) and the ATC subclass is taken from the WHO-DD code (first 3 characters).

Bayer Drug Groupings (BDG) will be used to select concomitant medications of special interest. The selected concomitant medications will be summarized by parent BDG, BDG and substance name. See the [main SAP section 6.1.2](#) for reference.

6.1.3 Study medication duration and exposure

Study medication duration and exposure will be summarized by treatment group and overall.

The duration of study medication (in days) is derived by calculating the study medication durations by the following formula: period (last dose date – first dose date + 1). Descriptive statistics of treatment duration as well as frequency counts by treatment duration categories will be presented. Dose titration by visit, dose titration sequence and reasons for up- and down-titration by visit and dose will also be summarized using frequency counts from titration phase of LTE period.

The formula for compliance is:

$$\frac{(\text{Total dispensed} - \text{total returned})}{(\text{Days between visits} \times \text{dose}[\# \text{ of pills}])} \times 100$$

= What was taken / What should've been taken

x 100 = % Compliance

6.2 Efficacy

In the LTE phase, the following endpoints will be described:

- mRSS
- Pulmonary function testing:
 - FVC% predicted
 - FVC (l)
 - DLco% predicted
 - DLco (mmol/min/kPa)
- PROs / HRQoL:
 - Scleroderma Health Assessment Questionnaire (SHAQ)
 - Short Form 36 (SF-36)
 - Patient-Reported Outcomes Measurement Information System (PROMIS)-29
 - University of California, Los Angeles, Scleroderma Clinical Trial Consortium Gastrointestinal Scale (UCLA SCTC GIT) 2.0.
- Worsening of end-organ disease (cardiac, renal, pulmonary, gastrointestinal & digital ischemia)
- Digital ulcer net burden
- Proportion of patients developing new digital ulcers
- Evaluate digital ulcers for patients with and without DUs at baseline by line plots
- All cause mortality
- Composite endpoint will be assessed from Week 52 to the end of the study (in addition, each individual endpoint will be described separately):
 - mRSS progression (defined as an increase in mRSS by > 4 units or >=20%)
 - worsening of FVC (defined as an absolute change of FVC% predicted \leq -10)

- new organ involvement (as defined in CRISS Step 1 main SAP).

Main study phase and LTE phase data will be shown in summary tables. Change from baseline and change from Week 52 (which is the baseline for the LTE analysis) will be shown. Progression/regression/improvement/worsening rates will be assessed from Week 52 until the end of the study.

6.2.1 mRSS

- Summary statistics for mRSS
- mRSS progression rate (defined as increase in mRSS by > 5 units and $\geq 25\%$)
- mRSS regression rate (defined as decrease in mRSS by > 5 units and $\geq 25\%$)
- mRSS progression rate (defined as increase in mRSS by > 4 units or $\geq 20\%$)
- Percentage of subjects with $\geq 20\%$, 40% , or 60% improvement in mRSS
- Percentage of subjects with $\geq 20\%$, 40% , or 60% worsening in mRSS

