3.1.4 Definition of rescue therapy

During the LTE phase (ie, after completion of all efficacy- and safety-related procedures at Visit 12), except for the contraindicated nitrates or NO donors and PDE5 inhibitors, the addition of any other concomitant medication was at the discretion of the investigator.

Use of rescue therapy agents (4 agents: methotrexate, mycophenolate mofetil, cyclophosphamide or azathioprine are counted as defined in the main SAP) will be tabulated by therapy from Week 52 to the end of the study date and overall by timepoint.

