6.2.5 Subgroup analysis

Descriptive analyses of the primary efficacy outcome measure (change in mRSS from baseline to the end of the study and change in mRSS from Week 52 to end of study) will be performed for the following subgroups:

- region (North America, Europe and Australia/New Zealand, East Asia)
- gender (males/females)
- age (age < 65 years/age \geq 65 years)
- mRSS at baseline (10 - 16 units/17 - 22 units)
- disease duration at baseline (0 - 6 months, 7 - 12 months, 13 - 18 months)
- antibody at baseline:
 - SCL-70, RNA polymerase III; both positive, both negative, either one positive
 - Anti-centromere B; negative (< 10 U/mL) / positive (\geq 10 U/mL)
 - Anti-centromere B positive + SCL-70 and RNA polymerase III negative
 - Anti-centromere B positive + either SCL-70 or RNA polymerase III positive
- ILD (interstitial lung disease) per medical history (defined with preferred terms: interstitial lung disease and pulmonary fibrosis) at baseline (yes/no)
- FVC%, predicted at baseline (<50, 50-75, > 75)
- FVC%, predicted at week 52 (<50, 50-75, > 75)
- hsCRP elevated at baseline (\leq 3.0 mg/L, > 3.0 mg/L; and \leq 10.0 mg/L, > 10.0 mg/L)
- use of corticosteroids at baseline (yes/no)

- tendon friction at baseline (yes/no)
- mRSS at week 52 (<10 units/ 10 - 16 units/ 17 - 22 units/ >22 units)

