6.4.1 Adverse events and mortality

The incidence of AEs (includes incidence of TEAEs and incidence of post-treatment AEs) will be summarized using MedDRA (version 21.1) preferred terms grouped by primary system organ class. The version number of MedDRA relevant for study evaluation will be stored in the study database.

The incidence of treatment-emergent AEs (TEAEs) occurring during the LTE phase will be tabulated by treatment groups defined for LTE phase. More specifically, AEs are considered to be treatment-emergent if they have started or worsened after first application of study drug up to 2 days after end of treatment with study drug.

An overall summary of the number and percentage of patients with TEAEs will be presented by treatment groups for events from Week 52 to the end of the study. This summary will include the number and the percentage of patients with drug-related TEAEs, treatment emergent serious adverse events (TESAEs), drug-related TESAEs, maximum intensity, AEs leading to permanent discontinuation and AEs with outcome of death.

Incidences of subjects with TEAEs occurring during LTE phase will be summarized by treatment arm and MedDRA terms using frequency tables for the following AE types:

- TEAEs
- Drug-related TEAEs
- TESAEs
- Drug-related TESAEs
- TEAEs of special interests
- Drug-related TEAEs of special interest

Tables for maximum intensity of TEAEs, TESAEs and drug-related TEAEs will be provided.

TEAEs which occurred during the main phase and were ongoing (i.e. not reported as “recovered/resolved” or “recovered/resolved with sequelae”) at the entry in LTE phase will be summarized.

Incidences of TEAEs and TESAEs per 100 person-years will be tabulated. The rate per 100 person-years is calculated as

$$\text{Rate per 100 person-years} = \text{number of events} / (\text{total drug exposure in years} / 100),$$

where 365.25 days are taken as one year.

The incidence of all post-treatment AEs (i.e., AEs occurring more than 2 days after end of treatment with study drug) will be tabulated separately.

AEs with outcome of death will be tabulated from Week 52 to the end of the study.

SAEs, deaths, AE leading to discontinuation and AEs of special interest (as defined in the [protocol Section 7.5.1.6](#)) will be listed. The date, relative day (to study medication) will be included.

Further summaries of AEs by intensity and outcome, may be provided, consistent with Bayer Global Medical Standards.

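### Must the extension-phase SAP state whether skin-score progression and the composite count at any visit or only at the last one?

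*SAP*

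**What the plan says.** The composite in SAP section 6.2 combines an mRSS item, an FVC item and new organ involvement. Its timing is "Composite endpoint will be assessed from Week 52 to the end of the study". For the separate rates the SAP writes "Progression/regression/improvement/worsening rates will be assessed from Week 52 until the end of the study".

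Two different skin limits appear. The composite uses "mRSS progression (defined as an increase in mRSS by > 4 units or >=20" per cent, joined by an or. Section 6.2.1 also lists a stricter limit, "mRSS progression rate (defined as increase in mRSS by > 5 units and" at least 25%.

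Neither section says which visit or visits decide whether a patient has the event. Section 4.5.1 settles repeat measurements within one visit only. Section 3.2 defines the end of the study for countries and for the whole trial, not for a patient.

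For the main phase the protocol is clearer. Section 8.6 describes mRSS progression as deterioration up to any assessment, and section 8.4.2.2 analyses time to first progression with a log-rank test.

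**The concern.** The SAP attaches similar end-of-study wording to different kinds of quantity. For deaths it covers every event in the period: "AEs with outcome of death will be tabulated from Week 52 to the end of the study". In the subgroup section it goes with a change score, "change in mRSS from baseline to the end of the study and change in mRSS from Week 52 to end of study", which needs a single end value. A patient who crosses the limit at Week 76 and is back below it at the last visit is therefore an event on one reading and not on the other.

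Follow-up length adds to this. The study was stopped early, so patients have different numbers of three-monthly skin scores, and a crude any-visit proportion rises with the number of scores. Elsewhere the SAP does deal with time: "Incidences of TEAEs and TESAEs per 100 person-years will be tabulated", a Kaplan-Meier plot for time to end of treatment, and rescue use tabulated "from Week 52 to the end of the study date and overall by timepoint". It offers nothing similar for these rates.

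At stake is whether the progression percentages in the report addendum can be interpreted, and whether the counting rule could be picked after the data are seen.

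**Working it through.** **No LTE rate to reproduce.** The documents state no expected LTE progression or composite rate. The SDs come from protocol section 8.6. Its Table 8-2 does reproduce: with SD 8, difference 4 and two-sided 5%, the noncentral t gives 70.6% power at 51 per group and 80.2% at 64, against 70% and 80% stated.

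**Inputs from the documents.** SD of mRSS change 7.2 at 6 months and 8.4 at 12 months (Table 8-1), and 8.0 for the sample size. LTE skin scores are about every 12 weeks.

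**Inputs that must be assumed.** Week 52 score, mean change, number of visits and between-visit correlation. The Table 8-1 SDs used here are from placebo arms of other trials and measure change from trial baseline; applying them to riociguat-treated patients after Week 52 is also an assumption.

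**Number of visits.** Amendment 7 (17 APR 2018) already draws on main-phase results, so the last Week 52 visit was earlier. From then to the end of MAR 2019 is 50 weeks. A patient randomised by 23 MAY 2016 reaches Week 52 by about 22 MAY 2017, leaving 97 weeks. Less the 30-day follow-up, this allows 3 or 7 scheduled visits plus the termination visit: 4 or 8 assessments.

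**Last visit, closed form.** With no mean change, the probability is 1 − Φ(threshold / SD). For the composite's skin item:
- Week 52 score 14: threshold 20% × 14 = 2.8, so 1 − Φ(2.8/8.4) = 36.9%.
- Score 16: threshold 3.2, giving 35%.
- Score 20 or more: the 4-unit limit applies, giving 32%.

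**Any visit, simulation.** This needs a correlation structure. One choice is a random walk plus measurement error fitted to both SDs:
- walk variance = (8.4² − 7.2²)/6 = (70.56 − 51.84)/6 = 3.12 per month;
- error variance in a change = 51.84 − 6 × 3.12 = 33.12, so SD per score = √(33.12/2) = 4.07.

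Results for the composite's skin item, with integer scores, Week 52 score 15 and no mean change unless stated:

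| Setting | Assessments | Any visit | Last visit | Gap (points) |
|---|---|---|---|---|
| Walk plus error | 4 | 61% | 37% | 24 |
| Walk plus error | 8 | 72% | 39% | 33 |
| Walk plus error, mean change −2 a year | 4 | 55% | 29% | 26 |
| Walk only, SD 8.4 at 12 months | 4 | 55% | 38% | 17 |
| Both SDs halved | 4 | 46% | 26% | 20 |
| SD 8.0, correlation 0.9 | 4 | 50% | 38% | 13 |
| SD 8.0, correlation 0.9 | 2 | 45% | 38% | 7 |

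Across Week 52 scores of 10 to 22 and correlation structures from pure random walk to equal correlation of 0.5 to 0.9, four visits with no mean change give a gap of about 12 to 31 points. The stricter limit gives 46% against 25% with four assessments in the walk-plus-error setting. No composite rate can be computed, because the documents give no SD for FVC change and no organ-event rate.

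**Which reading the text supports.**
- Section 6.2 describes a period over which the rates are assessed. A continuous change score, as in section 6.2.5, has to have an end value; an event rate does not.
- Section 6.2.2 counts subjects who experience FVC worsening, which is event language.
- The organ item of the composite borrows CRISS Step 1. Protocol section 8.4.2.2 applies that step when a patient develops a listed event, so a composite read only at the last visit would fit poorly.
- The SAP is based on this protocol, whose own progression measure uses any assessment and time to first event.
- SAP section 4.5 places derived variables in a separate specification document.

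**The case for a change.** The best case for a change is that the protocol's main-phase rule is not carried into the LTE SAP. The composite and its looser skin limit do not appear in the protocol, and the main-phase SAP, not among the documents here, is cited within this endpoint only for organ involvement. The extension becomes open-label and main-phase results are already known, so an unwritten rule could be settled with the data in view. Showing each component separately does not help, since the skin item has the same gap. One added sentence would cost little.

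Part of this stands. No sentence fixes the visit rule, and no setting tested removes the difference between the readings. A crude any-visit proportion also has no fixed time meaning without the length of follow-up beside it.

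The rest is weaker. That two analysts would report different rates is conjecture, because neither the derivation specification nor the main-phase SAP can be seen. The denominator is not fully open: sections 4.1 and 5.1 set one population for all LTE analyses, leaving only how to count patients with no score after Week 52. A competing-risk table with fixed landmark weeks would be more than a descriptive extension needs.

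**Conclusion.** No change is called for. The omission is real, but it is detail left to the derivation stage of a descriptive analysis, and the surrounding text points analysts towards counting an event at any assessment after Week 52. SAP section 6 declares all LTE results purely exploratory and warns against comparing the two groups, since the original randomisation is not preserved. Both groups should also have similar potential follow-up. No significance level, power or decision depends on the choice.

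The size is an illustration: about 12 to 31 points between the readings for the composite's skin item over four visits with no mean change. It is smaller with fewer visits (7 points in the two-visit example) and larger with more (33 points in the eight-assessment example). It rests on other trials' SDs and on assumed Week 52 scores, visit counts and correlations. The 61% and 37% pair is one such setting; it is not a composite rate and does not apply to the stricter skin limit. A reader of the extension results should check which counting rule a progression table uses before quoting its percentage.

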6.2.2 Pulmonary function testing

- Summary statistics for pulmonary function testing (FVC (forced vital capacity)% predicted, FVC (l), DLco % predicted, DLco (mmol/min/kPa)
- Number of subjects who experience worsening (absolute and relative decline) in FVC% predicted by 15% or more
- Number of subjects who experience worsening (absolute and relative decline) in FVC% predicted by 10% or more

6.2.3 PROs / HRQoL

- SF-36 (Variables: Bodily Pain, General Health, Mental Health, Physical Functioning, Role Emotional, Role Physical, Social Functioning, Vitality, Mental Component Score, Physical Component Score, Mental Health Enhanced score and Health Utility Index) [1.] Norm-based scores in addition to scores 0-100 will be reported.
- SHAQ (VAS variables: pain, intestinal problems, breathing problems, Raynaud's symptoms, finger ulcers and overall severity). All the VAS scores will be converted to 0-3 scale by multiplying results in mm by factor 0.03 and rounding by 0.1 decimals [2.]
- Gastrointestinal involvement as assessed by University of California, Los Angeles, Scleroderma Clinical Trial Consortium Gastrointestinal Scale (UCLA SCTC GIT) 2.0 instrument
- Patient-Reported Outcomes Measurement Information System (PROMIS)-29 (subset of sites belonging to English-speaking countries) [3.]

- Number and proportion of patients with HAQ-DI improvement ($\Delta\text{HAQ-DI} \leq -0.21$) or non-improvement ($\Delta\text{HAQ-DI} > -0.21$)
- Number and proportion of patients with HAQ-DI improvement ($\Delta\text{HAQ-DI} \leq -0.25$) or non-improvement ($\Delta\text{HAQ-DI} > -0.25$)

6.2.4 Worsening of end-organ diseases

Possible worsened adverse events (cardiac, renal, pulmonary, gastrointestinal & digital ischemia) in the LTE phase identified by certain SOC and PT will be reviewed by an (internal) medical expert applying the definitions of “worsening of end-organ disease” as defined in the Adjudication Committee charter. After evaluation of medical expert, investigators will be asked to confirm the finding. Worsened events, which are confirmed by investigators, will be marked in Rave for reporting. In contrast, in the main phase, adjudication of clinical events was done by an (external) adjudication committee. Thus, only events from the LTE phase will be tabulated. Careful interpretation is necessary when comparing the results from the main phase and the LTE phase.

6.2.5 Subgroup analysis

Descriptive analyses of the primary efficacy outcome measure (change in mRSS from baseline to the end of the study and change in mRSS from Week 52 to end of study) will be performed for the following subgroups:

- region (North America, Europe and Australia/New Zealand, East Asia)
- gender (males/females)
- age (age < 65 years/age \geq 65 years)
- mRSS at baseline (10 - 16 units/17 - 22 units)
- disease duration at baseline (0 - 6 months, 7 - 12 months, 13 - 18 months)
- antibody at baseline:
 - SCL-70, RNA polymerase III; both positive, both negative, either one positive
 - Anti-centromere B; negative (< 10 U/mL) / positive (\geq 10 U/mL)
 - Anti-centromere B positive + SCL-70 and RNA polymerase III negative
 - Anti-centromere B positive + either SCL-70 or RNA polymerase III positive
- ILD (interstitial lung disease) per medical history (defined with preferred terms: interstitial lung disease and pulmonary fibrosis) at baseline (yes/no)
- FVC%, predicted at baseline (<50, 50-75, > 75)
- FVC%, predicted at week 52 (<50, 50-75, > 75)
- hsCRP elevated at baseline (\leq 3.0 mg/L, > 3.0 mg/L; and \leq 10.0 mg/L, > 10.0 mg/L)
- use of corticosteroids at baseline (yes/no)

- tendon friction at baseline (yes/no)
- mRSS at week 52 (<10 units/ 10 - 16 units/ 17 - 22 units/ >22 units)

6.3 Pharmacokinetics/pharmacodynamics

BAY 63-2521 and M1 trough concentrations will be summarized per visit, according to previous dose for trough concentrations. During LTE phase PK was assessed only through visits from V12 to V17. The analyses will be focused on descriptive statistics. The following statistics will be calculated for each of the sampling points: arithmetic mean, standard deviation and coefficient of variation (CV), geometric mean, geometric standard deviation (re-transformed standard deviation of the logarithms), and CV, minimum, median, maximum value and the number of measurements. Boxplot of concentration of BAY 63-2521 by visit will be created.

Means at any time will only be calculated if at least 2/3 of the individual data were measured and were above the limit of quantification (LOQ). For the calculation of the mean value a data point below LOQ will be substituted by one half of the limit.

